7.6.2 Survival Follow-Up

After disease progression is documented, patients will be followed every 3 months (\pm 1 month) for survival (e.g., date and cause of death) for up to 3 years from the start of treatment or death whichever comes first. **A VeriStrat serum sample will be collected from all patients at the first Follow-Up Visit after disease progression.** For subsequent follow up, patients may be contacted during outpatient visits or by telephone.

8. DRUG FORMULATION, AVAILABILITY, ADMINISTRATION, AND TOXICITY INFORMATION

8.1 Everolimus

Investigational Product	Dosage Form and Strength	Manufacturer
Everolimus	5 mg	Novartis

8.1.1 Labeling, Packaging, and Supply

Everolimus will be supplied in 5mg tablets by Novartis Pharmaceuticals as individual patient packs.

At the beginning of every cycle, patients will be dispensed sufficient supplies until the next visit. Study drug compliance will be assessed at each patient visit. The research staff will count and document the amount of study drug taken and returned by the patient.

All study drugs must be kept in a secure place under appropriate storage conditions. Storage conditions for everolimus are included on the product label.

SCRI Innovations must be granted access on reasonable request to check drug storage, dispensing procedures, and accountability records.

8.1.2 Preparation and Administration of Everolimus

Everolimus is administered orally by the patients themselves, on an outpatient basis.

CONFIDENTIAL

STUDY DRUG(S): EVEROLIMUS
FINAL PROTOCOL DATE: 19 JUNE 2014

SCRI INNOVATIONS STUDY NUMBER: BRE 212
VERSION 1.0

Everolimus should be taken by the patient once daily, at the same time every day, either consistently with food or consistently without food. Dietary habits around the time of everolimus intake should be as consistent as possible throughout the study. Each dose of everolimus should be taken with a whole glass of water. Everolimus pills should be swallowed whole, and not chewed or crushed.

For patients unable to swallow tablets, everolimus should be dispersed completely in 1oz of water by gently stirring. The glass should then be rinsed completely with another ounce of water and swallowed to ensure the entire dose is administered.

If vomiting occurs, no attempt should be made to replace the vomited dose.

8.1.3 Precautions and Risks Associated with Everolimus

Precautions and risks are located in the everolimus IB.

8.2 Anti-estrogen Therapy

Patients will be prescribed the last anti-estrogen therapy received prior to study entry. This medication (tamoxifen, fulvestrant, anastrozole, letrozole, exemestane, toremifene, or LHRH agonists in conjunction with anti-estrogen therapy) is to be administered in accordance with the directions on the label. Please refer to the US Package Insert for detailed information on how to administer medication.

8.2.1 Labeling, Packaging, and Supply of Anti-estrogen Therapy

See the appropriate anti-estrogen package insert or product information.

SCRI Innovations or its representatives must be granted access on reasonable request to check drug storage, dispensing procedures, and accountability records.

8.2.2 Preparation and Administration of Anti-estrogen Therapy

Refer to the appropriate anti-estrogen package insert or product information for detailed information on the preparation and administration associated with the use of the medication.

8.2.3 Precautions and Risks Associated with Anti-estrogen Therapy

Please refer to the appropriate package insert for detailed information on related risks.

8.3 Accountability for All Study drugs

The Principal Investigator (PI) or designee is responsible for accountability of all used and unused study drug supplies at the site.

All study drug inventories must be made available for inspection by the monitor, Sponsor or representatives of the aforementioned and regulatory agency inspectors upon request.

At the end of the study, all SCRI Innovations Drug Accountability Record Form(s) will be completed by the site and copies will be sent to the SCRI Innovations Regulatory Department. Study drug supplies must not be destroyed unless prior approval has been granted by the Sponsor or its representative. Please contact SCRI Innovations regarding disposal of any study drug.

CONFIDENTIAL

STUDY DRUG(S): EVEROLIMUS
FINAL PROTOCOL DATE: 19 JUNE 2014

SCRI INNOVATIONS STUDY NUMBER: BRE 212
VERSION 1.0

9. RESPONSE EVALUATIONS AND MEASUREMENTS

Response and progression will be evaluated in this study using the Response Evaluation Criteria in Solid Tumors (RECIST) Version 1.1 (see Appendix E). Lesions are either measurable or non-measurable according to the criteria. The term “evaluable” in reference to measurability will not be used, as it does not provide additional meaning or accuracy.

10. STATISTICAL CONSIDERATIONS

10.1 Statistical Design

This is a multi-centered, open-labeled, Phase II study in MBC. The patient population includes locally recurrent or MBC patients with cytologically or histologically confirmed hormone receptor-positive breast cancer who have demonstrated disease progression on prior anti-estrogen therapy or therapies. Eligible patients must have evaluable or measurable disease per RECIST v1.1.

10.2 Sample Size Considerations

Results from the recently published BOLERO-2 study reported a median PFS of 2.8 months (as assessed by the treating investigator) that improved to 6.9 months as a result of the addition of everolimus in patients treated with exemestane after failing the NSAI therapy (Baselga J. et al. 2012). A similar median PFS is predicted in this study’s patient population that is based on similar inclusion criteria. It is anticipated that everolimus in combination with the last anti-estrogen therapy on which the patient demonstrated disease progression, will result in an increase in median PFS from 2.8 months to 5 months in this refractory population.

Based on the above assumptions, given a follow-up period of 12 months after the completion of enrollment (18 months), with a 5% alpha and a one-sided test of hypothesis, a sample size of 42 will provide 80% power to detect an improvement in median PFS from 2.8 months to 5 months in the patients treated with the combination of everolimus with anti-estrogen therapy. Allowing for 8-10% inevaluable patients, the total number of patients to be enrolled is 46 patients.

Sample size calculations are based on SWOGSTAT online sample size calculator for one-arm non-parametric survival endpoints (http://www.swogstat.org/stat/public/one_nonparametric_survival.htm).

10.3 Analysis Population

The following analysis populations will be used:

- Efficacy Evaluable Population is defined as all patients who receive at least 1 cycle of study treatment and have at least one post-baseline assessment. (Patients who discontinue treatment during Cycle 1 will not be replaced in the study.)
- Safety Population is defined as all patients who have received any dose of study treatment.

CONFIDENTIAL

STUDY DRUG(S): EVEROLIMUS
FINAL PROTOCOL DATE: 19 JUNE 2014

SCRI INNOVATIONS STUDY NUMBER: BRE 212
VERSION 1.0

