2.4 Secondary Endpoints

The secondary endpoints of this study are:

- Overall response rate in the subset of patients with measurable disease.
- Clinical benefit rate (Complete response (CR) + Partial response (PR) + Stable disease (SD) x 6 months).
- Duration of response (DOR).
- Percentage of patients progression-free at 4 and 6 months.
- Overall survival (OS).
- Safety and tolerability of everolimus with an anti-estrogen therapy.

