3. STUDY PATIENT POPULATION AND DISCONTINUATION

3.1 Inclusion Criteria

Patients must meet all of the following criteria in order to be included in the research study:

1. Histologic diagnosis of unresectable, locally recurrent or MBC.
2. ER and/or PR-positive tumors with staining by immunohistochemistry (IHC) based on the most recent biopsy.
3. Only 1 previous chemotherapy regimen for MBC. Patients progressing while receiving adjuvant endocrine therapy or progressing <12 months from completion of adjuvant endocrine therapy are eligible.

CONFIDENTIAL

STUDY DRUG(S): EVEROLIMUS
FINAL PROTOCOL DATE: 19 JUNE 2014

SCRI INNOVATIONS STUDY NUMBER: BRE 212
VERSION 1.0

4. Progressed on anti-estrogen therapy (tamoxifen, fulvestrant, anastrozole, letrozole, exemestane, toremifene, or LHRH agonists in conjunction with anti-estrogen therapy) defined as:

- Recurrence while on, or within 12 months of end of anti-estrogen therapy for early stage breast cancer, or
- Progression while on, or within one month of anti-estrogen therapy for locally advanced or metastatic breast cancer.

Note: No washout for anti-estrogen therapy required.

Anti-estrogen therapy does not have to be the last treatment prior to study entry.

5. Post- menopausal or pre/peri-menopausal women on tamoxifen. LHRH agonists may be used to render ovarian suppression with postmenopausal ranges of estradiol or FSH per institutional guidelines.

6. HER2-negative breast cancer, defined as follows:

- Fluorescent In Situ Hybridization (FISH)-negative (FISH ratio <2.0), or
- IHC 0-1+, or
- IHC 2-3+ AND FISH-negative (FISH ratio <2.0).

7. Measureable disease as measured by Response Evaluation Criteria in Solid Tumors (RECIST) criteria version 1.1 (See Appendix E) or evaluable bone lesions, lytic or mixed, in absence of measureable disease by RECIST criteria.

8. Adequate hematologic function, defined by:

- Absolute neutrophil count (ANC) $\geq 1.5 \times 10^9/L$
- Platelet count $\geq 100 \times 10^9/L$
- Hemoglobin $>9 \text{ g/dL}$.

9. Adequate liver function, defined by:

- Aspartate aminotransferase (AST) and alanine aminotransferase (ALT) $\leq 2.5 \times$ the upper limit of normal (ULN) or $\leq 5 \times$ ULN in presence of liver metastases)
- Total bilirubin $\leq 1.5 \times$ ULN.

10. Adequate renal function, defined by:

- Serum creatinine $\leq 1.5 \times$ ULN or calculated creatinine clearance of $\geq 40 \text{ ml/min}$.

CONFIDENTIAL

STUDY DRUG(S): EVEROLIMUS

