10.4.2 Efficacy Analysis

All efficacy analyses will be performed using the Efficacy Evaluable Population.

- Overall Response Rate (ORR) is defined as the proportion of patients with observed complete response (CR) or partial response (PR) according to the RECIST v1.1 criteria.
- Clinical Benefit Rate (CBR) is defined as the proportion of patients with CR, PR or SD x 6 months according to the RECIST v1.1 criteria.
 - For ORR and CBR, patients without a post-baseline tumor assessment will be classed as not evaluable (NE) and considered as non-responder.
- Progression Free Survival (PFS), defined as the time from the first day of study drug administration (Day 1) to disease progression (event) as defined by the RECIST v1.1 criteria, or death (event) on study. Patients who are alive and free from disease progression will be censored at the date of last tumor assessment. Patients who receive non-protocol therapy (subsequent therapy) prior to incurring an event will be censored at the date of last tumor assessment prior to the start of subsequent therapy. Patients who do not have a post-baseline tumor assessment will be censored at the date of first treatment (Day 1).
- Overall Survival (OS), defined as the time from the first day of study drug administration (Day 1) or death on study. Patients who are alive will be censored at the date of last known date alive.
- Duration of Response (DOR), is defined as the time from the first date of CR or PR to disease progression or death as defined by the RECIST v1.1 criteria. Patients who are alive and free from disease progression will be censored at the date of last tumor

CONFIDENTIAL

STUDY DRUG(S): EVEROLIMUS
FINAL PROTOCOL DATE: 19 JUNE 2014

SCRI INNOVATIONS STUDY NUMBER: BRE 212
VERSION 1.0

assessment. Patients who receive non-protocol therapy (subsequent therapy) prior to incurring an event will be censored at the date of last tumor assessment prior to the start of subsequent therapy. Only those patients who achieved CR or PR will be included in the summaries of DOR.

- Percentage of patients progression-free at 4 and 6 months, defined as the proportion of patients who are progression-free as defined by the RECIST v1.1 starting from the date of their first treatment.

For ORR and CBR, the estimates and the associated 95% CI (based on both asymptotic normal approximation and exact binomial methods) will be calculated.

Best overall response will be tabulated: CR, PR, SD, PD and not evaluable (NE).

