Efficacy Assessment Timepoints:	
Response Assessment Every 2 Cycles Patients will be reevaluated for response to treatment after every 2 cycles of treatment, prior to the start of odd-numbered cycles.
 
End of Study Treatment. The follow-up evaluations required after treatment ends (due to disease progression, or once the patient is discontinued due to unacceptable toxicity or decision to discontinue treatment by the patient or the study physician) are specified in Appendix D.
 
Follow-up for Patients Who Discontinue Prior to Disease Progression Patients who discontinue study treatment prior to the occurrence of disease progression will be followed every 3 months (\pm 1 month) from the date of last dose of study drug until disease progression or for up to 3 years from the start of treatment whichever comes first. Assessments at these visits will be performed as described in Appendix D.
 
Survival Follow-up After disease progression is documented, patients will be followed every 3 months (\pm 1 month) for survival (e.g., date and cause of death) for up to 3 years from the start of treatment or death whichever comes first.

Efficacy Endpoints:		
  
 	Endpoint	Primary Analysis Population	Other Analysis Population	
   
 Primary	PFS	Efficacy Evaluable	Safety	
 
 Secondary	OS, DOR, ORR, CBR	Efficacy Evaluable	Safety	
  
					Endpoint	Primary Analysis Population	Other Analysis Population	Primary	PFS	Efficacy Evaluable	Safety	Secondary	OS, DOR, ORR, CBR	Efficacy Evaluable	Safety											
	Endpoint	Primary Analysis Population	Other Analysis Population																									
Primary	PFS	Efficacy Evaluable	Safety																									
Secondary	OS, DOR, ORR, CBR	Efficacy Evaluable	Safety																									
Definition of Terms:																												
 Response	 Complete Response + Partial Response as best observed response  Complete Response + Partial Response, confirmed with weeks apart.  Other criteria, specify:																											

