No baseline assessment	Date of first treatment	Censored																										
PD documented between scheduled visits, did not die, and received no subsequent therapy	First date of evaluated overall response = PD	Event																										
PD documented between scheduled visits, did not die, but received subsequent therapy prior to incurring progression event	Date of last evaluable tumor assessment prior to start of subsequent therapy	Censored																										

	Death while on-study without previous PD, and received no subsequent therapy	Date of death	Event		
	Death while on-study and had previous PD, and received no subsequent therapy	First date of evaluated overall response = PD	Event		
	Death while on-study without previous PD, but received subsequent therapy prior to death event	Date of last evaluable tumor assessment prior to start of subsequent therapy	Censored		
	Death while on-study and had previous PD, but received subsequent therapy prior to PD event	Date of last evaluable tumor assessment prior to start of subsequent therapy	Censored		
	No progression, no death	Date of last evaluable tumor assessment	Censored		
	Treatment discontinuation for adverse event or other non-event reason	Date of last evaluable tumor assessment	Censored		
 Overall Response Rate (ORR)	Default: Estimates of rates in each treatment arm				
 Disease Control Rate (DCR)	 Difference in rates & 95% confidence interval between treatment arms  p-value, specify statistical test:				
 Clinical Benefit Rate (CBR)					
 Early Progression Rate (EPR)					
 Time To Progression (TTP)	Default: Estimates of medians in each treatment arm				
 Progression-Free Survival (PFS)	 Other quartiles or percentages of survival required, specify: PFS: @4 months and 6 months: percentages & 95% confidence intervals  Hazard ratio & 95% confidence interval between treatment arms, unstratified  p-value, specify statistical test:				
 Overall Survival (OS)					

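### The primary efficacy set is selected on what happens after Day 1, in a single arm read against a fixed median; the all-treated set should be primary and deaths exempted from Day 1 censoring

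*Protocol*

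**What the plan says.** **Which set is primary.** Protocol 10.3: "Efficacy Evaluable Population is defined as all patients who receive at least 1 cycle of study treatment and have at least one post-baseline assessment". Anyone stopping in Cycle 1 is not replaced. Protocol 10.4.2: "All efficacy analyses will be performed using the Efficacy Evaluable Population". In the endpoint table of SAP section 4, whose columns are endpoint, primary population and other population, the row for the primary endpoint reads "PFS Efficacy Evaluable Safety". OS, DOR, ORR and CBR have the same two populations. The Safety set is everyone who received any dose. SAP Tables 7, 8, 9 and 16 and Figures 1 and 2 are planned in both sets; Table 17 (median follow-up) is in Efficacy Evaluable (EE) only.

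**How patients without a scan are handled.** PFS in Protocol 10.4.2 runs from first dose to progression or death on study. The definition then adds: "Patients who do not have a post-baseline tumor assessment will be censored at the date of first treatment (Day 1". SAP 1.2 repeats this. The PFS table in SAP section 4 has a row "Death while on-study without previous PD, and received no subsequent therapy", which is an event at the date of death. That table has a row for no baseline assessment but none for no post-baseline assessment. For ORR and CBR, "patients without a post-baseline tumor assessment will be classed as not evaluable (NE) and considered as non-responder".

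**ORR denominator.** Protocol 2.4 lists "Overall response rate in the subset of patients with measurable disease", and inclusion criterion 7 also admits patients with "evaluable bone lesions, lytic or mixed, in absence of measureable disease by RECIST criteria". The ORR definition in 10.4.2 and SAP Table 7 do not carry the measurable-disease restriction.

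**Design figures.** Protocol 10.2 plans 42 evaluable patients (one-sided 5%, 80% power, median 2.8 against 5 months) and enrolls 46 to allow for 8-10% inevaluable. It does not say why patients would be inevaluable.

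**The concern.** A patient who progresses, dies or stops during Cycle 1 does not complete a cycle and so leaves the headline analysis, although the PFS clock has already started. In a randomized trial a control arm would lose similar patients. Here the result is read against a fixed external median, so any link between exclusion and prognosis goes straight into the estimate.

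The Safety set is the only check on this, and it is weakened by the Day 1 sentence. A patient who dies before any scan fits both the censoring sentence and the SAP row that counts the death. If the sentence is followed, that death carries no Kaplan-Meier weight even in the all-treated analysis. Early progressions seen on a scan would still count there.

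Membership of EE is also unclear. Its definition asks for an assessment, while the censoring and not-evaluable rules speak of a tumor assessment. The first scheduled scan is at 8 weeks (Protocol 5.1.1, Restaging), so a patient who completes Cycle 1 but is never scanned is in EE on one reading and out on the other.

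**Working it through.** **1. The plan's own figures.** Take a one-sample test of S(2.8 months) under exponential PFS: S0 = 0.500 and S1 = exp(-ln 2 × 2.8/5) = 0.678. With the variance under the alternative, n = (1.645 + 0.842)² × 0.678 × 0.322 / 0.178² ≈ 42.4, and power at n = 42 is 79.6%. So 42 is reproduced to within one patient; the exact formula of the online calculator is not in the documents. Enrollment: 42/0.92 = 45.7, so 46. The implied exclusion is 4/46 = 8.7%.

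**2. Could four early failures occur?** Under the 2.8-month null, P(event within 28 days) = 1 - exp(-ln 2 × 0.920/2.8) = 20.4%. Under 5.0 months it is 12.0%. Of 46 patients that is about 9.4 and 5.5, more than four in either case.

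**3. Effect on the median, continuous dating.** Of the 4 excluded, let g be known progression-free at the median and 4 - g have failed early. Then S_EE(t) = (46 S(t) - g)/42, and the EE median is m × ln((21 + g)/46)/ln(0.5).

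| Excluded patients | EE median, true 2.8 | EE median, true 5.0 |
|---|---|---|
| 4 failures | 3.17 | 5.66 |
| 3 failures, 1 progression-free | 2.98 | 5.32 |
| 2 and 2 | 2.80 | 5.00 |
| 1 failure, 3 progression-free | 2.63 | 4.69 |
| 4 progression-free | 2.46 | 4.40 |

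If exclusion is unrelated to prognosis, there is no bias.

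**4. Effect on the 8-week scan grid.** Scans fall every 56 days = 1.84 months, with progression dated at the next scan. The 4- and 6-month rates are then the values at 16 and 24 weeks.

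| True median | Time | All treated | EE, 4 failures (× 46/42) | EE, 1 failure and 3 progression-free |
|---|---|---|---|---|
| 2.8 | 4 months | 40.2% | 44.0% | 36.9% |
| 2.8 | 6 months | 25.5% | 27.9% | 20.8% |
| 5.0 | 4 months | 60.0% | 65.8% | 58.6% |
| 5.0 | 6 months | 46.5% | 51.0% | 43.8% |

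The median moves in steps on this grid. In 40,000 simulated trials with four early failures excluded and a true 2.8, it was 3.68 months in 84% of trials (all treated) and 72% (EE). The EE median exceeded the all-treated median in 24% (true 2.8) and 51% (true 5.0), averaging the two times where the curve equals exactly 0.5. Taking the first time at or below 0.5 gives about 14-15% and 34%.

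**5. CBR and ORR.** If all four excluded patients lack clinical benefit, CBR is multiplied by 46/42 = 1.095; for example 18/46 = 39.1% reads 18/42 = 42.9%. For ORR, with M measurable patients (not given in the documents) and x excluded non-responders among them, the factor is M/(M - x). It is 1.00 at x = 0. At x = 4 it is 1.095 (M = 46), 1.125 (M = 36) or 1.182 (M = 26).

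**6. Deaths censored at Day 1.** In the Safety set, d such deaths multiply later Kaplan-Meier values by 46/(46 - d): 1.022 for one, 1.045 for two.

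**7. Will excluded patients be scanned?** Patients who stop without progression are followed every 3 months with CT (Protocol 7.6.1, Appendix D), so some become informative. The End of Study Treatment CT is waived if one was done in the previous 8 weeks, and that visit is 30 days after treatment ends (Appendix D, footnote k). A baseline CT taken b days before Day 1 qualifies if b + stop day + 30 ≤ 56, that is b + stop day ≤ 26. With b = 14, this covers patients who stop by day 12.

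**The case against.** The strongest reply is that both analyses are already planned. The SAP reports every efficacy endpoint in both sets and ticks no p-value or test for PFS, so changing the label only decides which column is the headline. That stands, and it limits the seriousness. It is also why no error rates are claimed here.

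The direction and size of the bias are unproven. The upper bound needs four failures seen within 28 days, before any scheduled scan, in patients with a life expectancy of at least 12 weeks. With a true median of 5.0, fewer than four such failures occur in about 18-19% of simulated trials. On the scan grid the median often does not move at all. All of this stands. But an unpredictable direction is itself a reason to headline the set that needs no assumption about why patients dropped out.

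Applying the not-evaluable and Day 1 rules within EE suggests that its assessment is not limited to scans, so the set may lose fewer patients than feared. That is the more natural reading, but neither document states it. On deaths, the same PFS definition counts death as an event and the SAP table agrees, so this is an unreconciled conflict rather than a settled rule. The scan waiver reaches only very early stops.

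Not replacing Cycle 1 dropouts does not create the selection; replacing them would increase it. Finally, the count of 42 in Protocol 10.2 and in the final-analysis trigger (Protocol 10.5.1, SAP 1.4) does not block the change. By the formula in step 1, power at 46 is about 82.7%, and patients with shorter follow-up are censored in the usual way.

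**Conclusion.** The concern holds and should be fixed, although it does not invalidate the trial. The text makes a set chosen on post-Day 1 events primary in an uncontrolled design, and its two rules for a patient who dies unscanned disagree.

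Assuming 46 treated, 4 excluded and exponential PFS, the headline median could read anywhere from 2.46 to 3.17 when the truth is 2.8, and from 4.40 to 5.66 when it is 5.0. The upper ends require every exclusion to be an early failure. CBR can be inflated by up to 9.5%, and ORR by an amount that depends on the unknown number of measurable patients. Confidence is high about the text; the direction of the PFS bias cannot be known in advance.

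**What to change.** In Protocol 10.3 and 10.4.2 and SAP sections 2 and 4:

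- Make the all-treated (Safety) set primary for PFS, OS and CBR. For ORR, make all treated patients with measurable disease at baseline primary, in line with Protocol 2.4. Keep EE as a sensitivity analysis.
- Limit the Day 1 censoring sentence (Protocol 10.4.2, SAP 1.2) to patients with neither a post-baseline scan nor a death. Death before the first scan, without subsequent therapy, is then an event at the date of death, as the SAP table already has it.
- State whether the assessment in the EE definition must be a tumor assessment.
- Add the Safety set to SAP Table 17.
- Remove the clause in SAP 1.2 that promises estimates for patients at the MTD. The trial has no dose-escalation part, and the clause matches neither planned population.

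The cost is wording in both documents, one added population in Table 17, and a measurable-disease denominator for the ORR rows of Table 7 (Table 6 already tabulates measurable and bone-only disease). The other tables and figures are already planned in both sets. The downside is a possibly less favorable headline estimate.
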